11.2 Assessment of Causality

The relationship of each reportable adverse event to the trial medication must be determined by a medically qualified individual according to the following definitions:

Unrelated - Where an event is not considered to be related to the IMP / intervention

Possibly Related – although a relationship to the IMP / intervention cannot be completely ruled out, the nature of the event, the underlying disease, concomitant medication or temporal relationship make other explanations possible.

Probably Related – the temporal relationship and absence of a more likely explanation suggest the event could be related to the IMP / intervention

Definitely Related – the known effects of the IMP, its therapeutic class or based on challenge testing suggests that the IMP / intervention is the most likely cause.

11.3 Procedure for Recording and Reporting Adverse Events

Cognitive Behavioural Therapy and Cognitive Behavioural Group Therapy are well established therapeutic interventions for anxiety and depression with a particularly good safety basis. However adverse reactions and events can occur (for example suicidal thoughts after exposure, dissociation, destabilisation, emergence of new feelings, strains in existing relationships, non-adherence to therapy structure). The severity of any of any occurring events will be assessed on the above 'Mild' / 'Moderate' / 'Severe' scale. If 'Mild' they are not required to be reported. If moderate or severe the procedure is followed as outlined in GMMH RDSOP41 Recording and Reporting Adverse Events for non-CTIMPs. All Adverse Events considered related to the trial as judged by a medically qualified investigator will be followed either until resolution, or the event is considered stable.

It will be left to the Investigator's clinical judgment to decide whether or not an AE is of sufficient severity to require the participant's removal from treatment. A participant may also voluntarily withdraw from treatment due to what he or she perceives as an intolerable AE. If either of these occurs, the participant will be followed-up and be given appropriate care under medical supervision until symptoms cease, or the condition becomes stable.

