11 SAFETY REPORTING

11.1 Adverse Events Definitions

Adverse Event (AE)	Any untoward medical or psychological
	occurrence in a participant receiving
	psychological therapy or other trial intervention
	and which does not necessarily have a causal
	relationship with this intervention. An adverse
	event can therefore be any unfavourable and

	unintended sign, symptom, or disease in any subject in a trial (including those in an untreated control group), whether or not considered related to the investigational psychological therapy/intervention.
Serious Adverse Event (SAE)	A serious adverse event is any untoward medical occurrence that:
	 results in death is life-threatening requires inpatient hospitalisation or prolongation of existing hospitalisation results in persistent or significant disability/incapacity results in suicidal thoughts
	Other 'important medical events' may also be considered a serious adverse event when, based upon appropriate medical judgement, the event may jeopardise the participant and may require medical or surgical intervention to prevent one of the outcomes listed above.
	NOTE: The term "life-threatening" in the definition of "serious" refers to an event in which the participant was at risk of death at the time of the event; it does not refer to an event which hypothetically might have caused death if it were more severe.
Adverse Reaction (AR)	All untoward and unintended responses to an investigational psychological therapy or other intervention. All adverse events judged by either the reporting investigator or the sponsor as having a reasonable causal relationship (e.g. definitely, probably or possibly related) to a psychological therapy/intervention qualify as adverse reactions.
Serious Adverse Reaction (SAR)	An adverse event that is both serious and, in the opinion of the reporting Investigator, believed with reasonable probability to be due to one of the trial treatments, based on the information provided.
Unexpected Adverse Reaction	An adverse reaction, the nature or severity of which is not consistent with the effects or consequences of the psychological therapy/intervention being investigated.
Suspected Unexpected Serious Adverse Reaction (SUSAR)	A serious adverse reaction, the nature and severity of which is not consistent with information in the MHRA approved Reference Safety Information

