Note: To avoid confusion or misunderstanding of the difference between the terms "serious" and "severe", the following note of clarification is provided

"Severe" is often used to describe intensity of a specific event, which may be of relatively minor medical significance.

"Seriousness" is the regulatory definition supplied is Serious Adverse Reaction.

The following grading criteria is used for the purpose of this protocol:

Mild: asymptomatic or mild symptoms, diagnostic observations only, no intervention indicated. Not interfering with everyday activities/functioning. Moderate: an event that is sufficiently discomforting to interfere with normal everyday activities. Minimal, local or non-invasive intervention indicated. Severe: an event that prevents normal everyday activities. Medically significant but not immediately life-threatening. Hospital or prolongation of hospitalisation indicated.

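### Section 11.3 filters adverse-event reporting by severity alone, so suicidal thoughts, which are serious under section 11.1, need not be reported if graded Mild

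*Protocol*

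**What the plan says.** Three parts of the protocol's safety section bear on this point.

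- **Seriousness (section 11.1, definitions table).** Five criteria make an event an SAE, followed by a catch-all for other important medical events. The last two of the five read "results in persistent or significant disability/incapacity results in suicidal thoughts". No intensity threshold is attached to suicidal thoughts.
- **Severity (the note that closes section 11.1).** The note warns against confusing serious with severe. It treats severity as intensity and seriousness as a separate regulatory definition. It then sets three grades, the lowest beginning "Mild: asymptomatic or mild symptoms, diagnostic observations only, no intervention indicated" and also requiring that everyday functioning is not disturbed.
- **Reporting (section 11.3).** Events that can arise in therapy are illustrated: "for example suicidal thoughts after exposure, dissociation, destabilisation" and others. Any "occurring events will be assessed on the above 'Mild' / 'Moderate' / 'Severe' scale". For the lowest grade, "If 'Mild' they are not required to be reported". For the rest, "If moderate or severe the procedure is followed as outlined in GMMH RDSOP41 Recording and Reporting Adverse Events for non-CTIMPs".

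Section 11.2 asks a medically qualified person to judge causality, but limits that duty to events that are reportable.

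**The concern.** The protocol separates seriousness from severity and then decides what is reported by severity alone. For most serious events this does no harm, because they could hardly be graded Mild. Suicidal thoughts are the exception. They are serious by definition here, the protocol foresees them, and their intensity can vary.

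What is at stake is the completeness of SAE reporting in women under secondary care for depression, anxiety or a puerperal disorder. Whether such an event reaches the sponsor as an SAE would turn on a subjective grade. There is little independent check on that grade: the Chief Investigator leads the sessions, has sole access to identifiable study data and writes up the study, and the protocol states that there is no steering group. The group is also small. One affected woman is 1/10 = 10% of the planned ten, or 1/6 = about 17% of the minimum six, so a single unreported case would change the SAE picture noticeably.

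**Working it through.** The protocol states no figure on this point, so there is nothing to recompute. The check is to apply the rules in order to one case: a participant has passing suicidal thoughts after a session, they call for no intervention, and they do not disturb her daily life.

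1. **Is it serious?** Section 11.1: yes. The criterion is met by the thoughts themselves, whatever their intensity.
2. **What grade may it receive?** Severity note in section 11.1: Mild fits, because the grade rests on mild symptoms, no intervention and no effect on functioning. Nothing bars that grade for an event that meets a seriousness criterion.
3. **Must it be reported?** Section 11.3: not at that grade. RDSOP41 is reached only from Moderate or Severe, and serious events are not carved out.
4. **Must causality be judged?** Section 11.2: no, because the duty covers reportable events only.
5. **Must it be followed up?** Section 11.3 follows events judged related to the trial until they resolve or stabilise, at any grade. That depends on a judgement of relatedness, which step 4 does not require for this event.
6. **Is there another route?** None was found that depends on seriousness. The risk pathway in section 2.1 and the session summaries with a brief risk assessment in sections 9.1, 9.3 and 10.6 are clinical-care routes. The report to the sponsor in section 10.5 concerns protocol deviations.

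Applying the same steps to the other listed criteria shows how wide the gap is:

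| Criterion in 11.1 | Can it plausibly be Mild? |
|---|---|
| Death | No; beyond the scale |
| Life-threatening | No; even the Severe grade stops short of this |
| Hospital admission or longer stay | No; this belongs to the Severe grade |
| Lasting or significant disability | Hardly; it implies impaired functioning |
| Suicidal thoughts | Yes, if no intervention is needed and functioning is intact |

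So one of the five listed criteria is clearly affected.

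**The case against.** The strongest reply is that the gap is narrow. Mild requires that no intervention is indicated. In this study a suicidal thought would come to the attention of a consultant psychiatrist, with a risk assessment recorded for each session and a pathway that begins with the care co-ordinator and the woman's own psychiatrist. Once any of that is triggered, Mild is hard to defend, and Moderate, which already covers a small non-invasive response, leads to RDSOP41. Section 6.2 also excludes women at active risk of self-harm. This stands as a limit on how often the gap would matter. It does not close it: the exclusion concerns active risk and not thoughts, and nothing forbids the Mild grade.

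A second reply is that RDSOP41 may itself require every SAE to be reported. That procedure is not part of the document, and the protocol sends readers to it only for Moderate or Severe events. Someone following section 11.3 would have no reason to open it for a Mild one.

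A third is that the sponsor is the Trust, which holds the clinical record and runs the risk pathway. This softens the consequence, since the Trust's clinicians may well know of the event. A note in the record is still not an SAE report and does not enter a trial count.

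**Conclusion.** The point holds. Sections 11.1 and 11.3 do not fit together for suicidal thoughts, and the reporting rule is wrong as written because it can leave a protocol-defined SAE unreported. The conclusion rests on the text alone and on one reading, that some suicidal thoughts can meet the Mild definition.

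Four stronger conclusions might be inferred, and the document supports none of them.

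- **That such events may not be reported at all.** Section 11.3 removes the requirement; it does not forbid a report. It also has severity assessed for all events, so it does not say that Mild ones go unrecorded.
- **That a definite number of SAEs would be lost.** The protocol gives neither the frequency of suicidal thoughts in this group nor the share that would be graded Mild. The loss could be zero. All that can be said is that counts could be understated.
- **That the study's safety conclusion would be wrong.** Section 3 plans symptom scales and a feedback questionnaire, with no safety objective or endpoint.
- **That the examples in section 11.3 define what is expected.** They are described only as events that can occur. Treating them as the expectedness reference could stop a related serious case of suicidal thoughts from counting as unexpected, a substantive choice that this point does not require.

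**What to change.** Reconcile the definitions and severity note in section 11.1 with the reporting rule in section 11.3, so that reporting follows seriousness. Wording such as this in 11.3 would do it:

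> Any event that meets a seriousness criterion in section 11.1 is reported as an SAE, whatever its severity grade. The exemption for Mild events applies to non-serious events only.

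Section 11.2 then needs no change for this purpose: once these events are reportable, its causality duty applies to them. The sponsor should check that RDSOP41 agrees with the new sentence.

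The cost is about one sentence in a protocol amendment and possibly a few more reports. Treatment, sessions, outcome measures and sample size are unaffected.

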12 DISSEMINIATION POLICY

12.1 Dissemination policy

The Chief investigator and the sponsor owns the data arising from the study.

On completion of the study, a Final Study Report will be prepared.

The study data will aim to be published in a relevant peer reviewed journal.

Once the data is analysed and the write up completed, participants are welcome to receive findings.

If the study is published in a journal, participants will also have the opportunity to receive a copy of the published paper.

12.2 Authorship eligibility guidelines and any intended use of professional writers

Authorship will be based on the international committee of medical journal editors authorship criteria.

13. APPENDICIES

13.1 Appendix 1 – Required Documentation

Curriculum vitae of Chief investigator

13.1 Appendix 2 – Proposed Schedule

Activity	Start			Pro	In ogress		Con	nplete											
		Dura tion	Feb 21	Mar 21	Apr 21	May 21	June 21	July 21	Aug 21	Sep 21	Oct 21	Nov 21	Dec 22	Jan 22	Feb 22	Mar 22	Apr 22	May 22	Jun 22
Obtain IRIS approval																			
Obtain ISRCTN registration																			
Recruit Participants																			
CBT Group and follow up																			
Write up and submission																			
Publication																			

13.3 Appendix 3 – Amendment History

Amendment No.	Protocol version no.	Date issued	Author(s) of changes	Details of changes made
1	1	14/03/21	[name]	
1.2	1.2	30/03/21	[name]	
1.3	1.3	16/05/21	[name]	
1.4	1.4	09/08/21	[name]	
1.5	1.5	10/08/21	[name]	Addition sponsor number
